# 7.7 Schedule of Events

		Visits							
Procedures	On Admission	Visit 1 Screening	Visit 2 Baseline (Day 1 – 0hrs)	Visit 3 Day 2 – 24hrs	Visit 4 Day 3 - 48hrs	Visit 5 Day 4 – 72hrs	Visit 6 Day 5 – 96hrs	Visit 7 30 Day Follow Up	Visit 8 180 Day Follow Up
Informed consent		Х							
Demographics		Х							
Medical history	X (RC)	Х							
Physical examination	X (RC)	Х	Х	Х	Х	Х	х		
Vital signs									
Height			Х						
Weight*			Х	Х	Х	Х	Х		
BMI			Х						
BP			Х	Х	Х	Х			
HR			Х	Х	Х	Х			
Concomitant medications		Х							
Ward round assessments by treating teams **	Х	Х	х	х	х	х	х		
ECG	X (RC)	Х							
Chest X-ray	X (RC)								
Laboratory tests									
FBC	X (RC)		Х	Х	Х	Х			
Urea & Electrolytes	X (RC)		Х	Х	Х	Х			

# Hull University Teaching Hospitals

Г						T		NHS
NTproBNP	X (RC)		X ( if not performed on admission)					
Eligibility assessment		Х						
Randomisation		Х						
Intravenous Furosemide infusion at 10mg/hr (standard of care)***	х		x	X****	X****	х		
Dispensing of trial drugs (Acetazolamide arm only)		x						
Acetazolamide given to the patient			x	Х	Х	Х		
Compliance with medication and diet sheet				X (previous day)	X (previous day)	X (previous day)	X (previous day)	
Oral intake – mL				X (previous day)	X (previous day)	X (previous day)	X (previous day)	
Urine output		Х	Х	X (previous day)	X (previous day)	X (previous day)	X (previous day)	
Urine electrolytes					X (previous day)		X (previous day)	
Likert breathlessness scale			Х	Х	X	Х	X	
Diet Sheet		X (x4 given to the patient)	Х	X (previous day)	X (previous day)	X (previous day)	X (previous day)	
Catheter sited (to measure urine output / jug used)		x						
Clinical assessment of congestion			X	X	X	X	X	
Ultrasound assessment of congestion			X				X	
Adverse event / reaction assessments				Х	Х	Х	Х	

# Hull University Teaching Hospitals

Time to clinical euvolaemia*****		х	Х	х	Х	Х	NHS	Trust
Length of stay						Х		
Cause specific re- hospitalisation						Х	Х	
Cause specific mortality						Х	Х	

RC – Routine care

\* Only weight assessment conducted daily

\*\* Includes assessment of vital signs, ongoing medical history, clinical examination, treatment plans, imaging procedures, involvement of allied healthcare professionals such as physiotherapist.

\*\*\* Patients may not immediately be started on the 'gold standard' treatment does (240mg/24hr infusion) but maybe changed on an infusion after consultant or specialist review

\*\*\*\* If the patient is deemed to not require standard of care by day 2 and has their diuretic treatment de-escalated efforts will be made to replace the patient

\*\*\*\*\* Defined as the absence of venous congestion or transition to oral diuretic therapy assessed by either the treating team or study team and documented in medical notes

# 7.8 Trial Visits

On admission

- Chest X-ray, blood tests (full blood count, biochemistry profile, NTproBNP), electrocardiogram, medical history and clinical examination – all part of routine care
- Started on intravenous furosemide (standard care). Patients may not immediately be started on the "gold standard" treatment dose (240mg/24hr infusion) but may be changed onto an infusion after consultant or specialist review.

Routine care consists of;

- Ward round assessments by treating teams
- Biochemical profile at least every 48 hours
- Echocardiography
- Daily assessment of weight and urine output
- Ongoing clinical input from treating teams depending on patient requirements.

#### Visit 1 - Screening

- Clinical examination and medical history to assess eligibility
- Informed Consent
- Demographics
- Randomisation
- Routine care as detailed above

Plus:

In the acetazolamide arm only:

• Acetazolamide will be prescribed on electronic drug card (ePMA) and dispensed by pharmacy clinical trials on a non-stock request for the patient and taken to drug cupboard store on ward by study doctor (250mg BD for 4 days taken in the morning and again 6 hours later - 8x 250mg tablets – 2x per day for 4 days per patient).

In both treatment arms:

- Diet sheet x4 given
- Catheter sited if patient consents and one is not already as part of routine care. If catheter not being used to measure urine output then a urine jug will be used

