# 7.2 Informed Consent

After the confirmation of eligibility and reconfirmation that the patient wishes to proceed, each potential participant will be informed of the aims, methods, nature of participation, anticipated benefits and potential hazards of the study, the alternatives to taking part and their right to withdraw consent at any stage without giving a reason and without prejudicing further treatment. The person taking consent will assume each participant to have capacity to give consent unless concerns are raised by the treating team or during the screening process (e.g. history of dementia or confusion on admission, nursing or medical concerns regarding cognition).

If concerns are raised, each participant will be assessed against the 2 stage capacity assessment defined by the Mental Capacity Act: 1) Is the patient able to make a particular decision? and 2) Is the person able to understand, retain and use information given to come to a decision and are they able to communicate this decision? If a person is deemed unable to give valid consent they are ineligible for the study.

The information will be provided to patient verbally and via the patient information sheet (PIS) which will be reviewed and approved by the Regional Ethics Committee (REC) and in accordance with GCP. Contact details for the study team will be provided. Patients will have the opportunity to ask any and all questions during and after the discussion before giving written consent.

The Chief Investigator (CI) will be jointly responsible for obtaining informed consent of all participants according to the approved protocol, principles of Good Clinical Practice and Declaration of Helsinki.

No trial procedure will be undertaken before informed consent is given. Data from procedures performed as part of routine care will not be collected before informed consent is given.

Should a patient lose capacity during the study attempts will be made to replace the patient in the recruitment total but data will be retained. In such an event, the results of symptom questionnaires and diet sheets will be recorded but not used in the final analysis.

Should a patient require re-consenting due to a significant alteration to the trial protocol or new information regarding the study, the IMP or the condition become available it is the joint responsibility of the PI and CI to inform the participants in a timely manner.

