# 7.3.1 Method of implementing the allocation sequence

Randomisation will be performed by the Simple Randomisation Service offered by Sealed Envelope TM (https://www.sealedenvelope.com). Patients will be randomised 1:1 to either A – acetazolamide or B – standard of care in a random permuted block of up to 50 patients (maximum recruitment). Randomisation will be accessed by the study doctors and the sponsors but randomisation will be performed by the study doctors at the point of consent. Sealed Envelope confirms allocation via email to the person performing the randomisation, a copy of which will also be sent to a member of the Research and Development team who will print the email and include in the CRF. The CI ([name]) can be contacted in an emergency via phone.

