# 7.4 Blinding

The trial will be an open label investigation without blinding for two reasons 1) we aim to collect pilot data to inform a larger blinded study 2) the primary endpoints and most secondary endpoints will not be susceptible to bias from unblinded treatment such as urine volumes and serum and urine electrolytes.

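### The protocol lets the urine collection method (catheter or jug) be chosen once the open-label arm is known, so section 7.4 is too strong in saying that unblinding cannot bias urine volumes

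*Protocol*

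**What the plan says.** **Order of steps.** Section 7.8, Visit 1, lists informed consent, then randomisation, then tasks by arm. Under the tasks common to both arms it has "Catheter sited if patient consents and one is not already as part of routine care" and "If catheter not being used to measure urine output then a urine jug will be used". The schedule in 7.7 puts consent, randomisation and the catheter row ("Catheter sited (to measure urine output / jug used") in the same Visit 1 column. Section 7.3.1 says "randomisation will be performed by the study doctors at the point of consent", with the allocation emailed to the person who randomises. Section 7.2 adds "No trial procedure will be undertaken before informed consent is given".

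**Blinding.** Section 7.4 begins "The trial will be an open label investigation without blinding for two reasons". The second reason given is that "the primary endpoints and most secondary endpoints will not be susceptible to bias from unblinded treatment such as urine volumes and serum and urine electrolytes".

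**Endpoint and analysis.** Section 3.4 defines net fluid loss from volume taken in and volume passed as urine. Section 11.1 takes both from the patient's diet sheet and the nursing record. Section 10.3.2 foresees two confounders, salt intake and loss of IV access, and its regression contains treatment, salt intake and hours of furosemide. Collection method appears neither there nor in the baseline table in 10.3.1.

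**The concern.** How a ward-recorded urine volume is collected may affect how much of it is recorded, and each millilitre not recorded moves net fluid loss by one millilitre. If the method is settled once doctor and patient know the arm, the expectation of extra diuresis on acetazolamide could influence whether a catheter is offered or accepted. If jugs also capture less than catheters, more complete capture in the acetazolamide arm would look like greater fluid loss, which is the hypothesised effect.

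Open-label conduct is defended in 7.4 partly on the ground that this cannot happen. The estimate is also meant to inform a larger trial (section 2), so a distortion here would be carried forward.

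**Working it through.** The plan gives no figure on this point, so there is nothing to reproduce. The check is of sequence first, then of possible size.

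**1. Can the arm be known when the method is chosen?**
- No trial procedure precedes consent (7.2), so a catheter sited for the study comes after consent.
- Randomisation takes place at the point of consent (7.3.1), and the doctor who randomises receives the allocation.
- Visit 1 lists the catheter after randomisation, under headings organised by arm (7.8).

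Together these mean that the arm is known, or can be known, when a study catheter is offered. No sentence states the order outright. A catheter already in place from routine care precedes allocation and is outside the point.

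**2. Does it reach a primary endpoint?** Yes for net fluid loss, through the urine term. No for serum chloride, which is a laboratory value.

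**3. How large could it be?** The documents give no capture rate and no catheter uptake, so all three inputs are assumptions:
- U, daily urine volume: 2500 to 3500 mL
- f, share of urine missed with a jug: 5% to 20%
- d, difference between arms in the share with a catheter: 10 to 50 percentage points

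Spurious difference per day = U × f × d.
- Low: 2500 × 0.05 × 0.10 = 12.5 mL/day, or 50 mL over 4 days
- Mid: 3000 × 0.10 × 0.30 = 90 mL/day, or 360 mL over 4 days
- High: 3500 × 0.20 × 0.50 = 350 mL/day, or 1400 mL over 4 days

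Against the 500 mL/day lower target in 10.1, these are 2.5%, 18% and 70%.

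**4. Effect of the timed collections.** Sections 7.8 (Visits 2 to 6) run timed 24-hour collections from 24 to 48 h and from 72 to 96 h, with a bottle for uncatheterised patients. If these lose nothing, only days 1 and 3 are exposed and the 4-day totals halve, to 25, 180 and 700 mL. Against the 2 L four-day target these are about 1%, 9% and 35%. The separate daily comparisons for days 1 and 3 are not helped.

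**5. Effect on the test.** With the stated minimum of 17 and 18 recruits and 10% and 20% drop-out, 17 × 0.9 = 15.3 and 18 × 0.8 = 14.4 are evaluable. The standard error is SD × √(1/15.3 + 1/14.4) = 0.367 × SD. Using the noncentral t with 27.7 degrees of freedom, the nominal 5% two-sided error becomes:

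| Bias (mL/day) | SD 500 mL | SD 1000 mL |
|---|---|---|
| 90 | 7.6% | 5.6% |
| 300 | 35% | 12% |

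**The case against.** The strongest reply is that the sequence is inferred. A list grouped by arm need not be a timetable, and the schedule gives no order within Visit 1. Agreement to a catheter might in practice be obtained during the consent discussion, before allocation. That stands as a limit: the protocol permits the choice to follow allocation but does not say that it must.

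The mechanism is also undocumented. Nothing says that a jug captures less than a catheter, and both arms receive the same furosemide infusion, so the reason to accept a catheter exists in both. The timed collections protect two of the four days. These points stand too, and they are why no size can be asserted.

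Three stronger readings are tempting and should be resisted:
- *Net fluid loss will be biased towards acetazolamide.* The documents show neither differential uptake nor differential loss. They show only that the route is open.
- *Both co-primary endpoints are compromised.* Serum chloride does not depend on urine collection.
- *Chance imbalance in method under simple randomisation is a further defect.* Chance variation in method is part of the outcome variance that the test already reflects. It is not bias.

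The reply that the analysis plan can deal with this later holds only in part. Such a plan could add a sensitivity analysis. But a method chosen after allocation is a post-randomisation variable, and adjusting for it is itself questionable. The order of steps and the blinding rationale belong to the protocol.

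**Conclusion.** The point holds as a possible, unquantified route to bias in one co-primary endpoint, for patients without a routine-care catheter. The claim in 7.4 is too strong for a ward-recorded urine volume.

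The range of about 12 to 350 mL/day rests entirely on assumed volumes, jug losses and uptake differences. The high end multiplies three extremes, and the timed collections probably make the true figure smaller. At the mid case the effect on the test is slight. The case for acting is that the remedy costs almost nothing, not that a material bias has been shown.

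**What to change.** - **Section 7.8, Visit 1:** agree and record the intended collection method after consent and before the randomisation request. This respects 7.2, since recording an intention is not a trial procedure on the patient. How long any catheter stays in place remains a clinical matter and needs no rule here.
- **Reporting:** show the recorded method by arm.
- **Section 10.3.2:** add this pre-randomisation method as a covariate in the net fluid loss regression.
- **Section 7.4:** limit the statement. For example: laboratory electrolytes are unlikely to be affected by knowledge of treatment; recorded urine volume could be, so the collection method is settled before allocation.
- **Cross-check:** present the change in body weight beside net fluid loss. Weight is already in the daily schedule, Visit 2 already specifies the same scales, and 10.3.3 already compares it between arms. It does not depend on how urine is collected.

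The cost is one reordered step, one case report form entry if none exists (the form is not shown), and one degree of freedom. With 20 per arm and the stated drop-out, 18 + 16 = 34 are evaluable. The present model (intercept, treatment, salt, hours of furosemide) leaves 34 − 4 = 30 residual degrees of freedom, and adding the method leaves 29. No extra procedure or visit is needed.

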# Visit 2 - Day 1 – 0 hours

Visit 2 can occur on the same day as screening if randomisation occurs before 12PM and the first dose of acetazolamide is given before 12PM (ACZ arm only).

- Furosemide infusion to continue
- Vital signs measured by nursing staff
- Bloods taken
  - o Urea and electrolytes
  - Full blood count
- Acetazolamide 250mg to be given by ward staff in the morning and again 6 hours later as prescribed on the electronic prescription (in ACZ group only)
- Ongoing input from treating team: ward round and any input that stems from that, regular observations from nursing staff, input from other health professionals if indicated (for example dieticians, physiotherapists, occupational therapists)
- Study doctor visit at +/- 2 hours from first dose of acetazolamide / randomisation (SoC arm)
   Clinical examination

- NTproBNP added to blood tests taken in the morning if not performed on admission
- Weight measured using the same set of scales
- Ultrasound assessment of congestion
  - Inferior vena cava diameter
- Patient assessed breathlessness using 5-point Likert breathlessness scale
- Diet sheet to be completed at 1800 (after evening meal)
- Patient provided with 24hr urine electrolyte bottle if not catheterised and instructed to begin collection at 24hrs from the first dose of acetazolamide the following day
  - Nursing staff to be informed

#  Visit 3 - Day 2 – 24 hours

- Furosemide infusion to continue if clinically indicated
  - If patient deemed to not require standard of care by day 2 and has their diuretic treatment de-escalated efforts will be made to replace patient. All data collected will be retained but patient will have "completed" the study early.
- Vital signs measured by nursing staff
- Bloods taken
  - Urea and electrolytes
  - o Full blood count
- Acetazolamide 250mg to be given by ward staff in the morning (24 hours after first dose) and 6 hours later (in ACZ group only) as per electronic prescription
- Ongoing input from treating team: ward round and any input that stems from that, regular observations from nursing staff, input from other health professionals if indicated (for example dieticians, physiotherapists, occupational therapists)
- Study doctor visit (24 hours +/- 2 hours from first dose of ACZ (ACZ arm) or randomisation (SoC arm)
  - Clinical examination and medical history
  - o Diet sheet collected from previous day
  - Fluid balance and urine output
  - o 24 hour urine collection to begin 24 hours from first dose of ACZ or randomisation
    - Patient asked to empty bladder or nursing staff to empty catheter bag and then begin urine collection
  - o Patient assessed breathlessness using 5-point Likert breathlessness scale

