#### Visit 6 - Day 5 – 96 hours

- Ongoing input from treating team: ward round and any input that stems from that, regular observations from nursing staff, input from other health professionals if indicated (for example dieticians, physiotherapists, occupational therapists)
- Study doctor visit (96 hours +/- 2 hours from first dose of ACZ (ACZ arm) or randomisation (SoC arm)
  - Clinical examination and medical history
  - Diet sheet collected from previous day
  - Fluid balance and urine output
  - Patient assessed breathlessness using 5-point Likert breathlessness scale
  - Urine collection to stop at 96 hours after first dose of ACZ or randomisation
  - Ultrasound assessment of congestion
    - IVC diameter

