# 8.5 Dosage schedules

The acetazolamide will be taken orally as it has good oral bioavailability (70-90%) reaching peak concentrations after 2 hours with a plasma half life of 4 hours. All other adjunctive diuretics are routinely given orally in the UK – e.g. Bendroflumethiazide, metolazone, dapagliflozin, empagliflozin.

ACZ will be given in the morning and again 6 hours later so that the maximal diuretic effect occurs in the daytime to reduce the chance of the patient waking in the night. The maximum daily dose is 500mg in maximum split doses of 250mg. There will be no individualised dosing. Duration of treatment is 4 days. Furosemide infusions will be continuous as long as is clinically indicated and replenished as and when required.

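### Study time starts at the first acetazolamide dose in one arm and at randomisation in the other, so patients randomised after midday get arm-dependent windows or conflicting visit rules

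*Protocol*

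**What the plan says.** In Section 7.8 the baseline visit is set as "Study doctor visit at +/- 2 hours from first dose of acetazolamide / randomisation (SoC arm", and the 24-hour visit as "Study doctor visit (24 hours +/- 2 hours from first dose of ACZ (ACZ arm) or randomisation (SoC arm". The 48, 72 and 96-hour visits repeat the pattern. Fluid balance and urine output are listed among the items for the study doctor at Visits 3 to 6.

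The 24-hour urine electrolyte collections follow the same split: "24 hour urine collection to begin 24 hours from first dose of ACZ or randomisation" for the first, and "Urine collection to stop at 96 hours after first dose of ACZ or randomisation" for the end of the second.

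Three other rules decide how far apart the two anchors lie:

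- Section 7.3.1: "randomisation will be performed by the study doctors at the point of consent". Section 7.8 lists randomisation under Visit 1. Neither limits the time of day.
- Section 8.5: "ACZ will be given in the morning and again 6 hours later".
- Section 7.8, Visit 2: "Visit 2 can occur on the same day as screening if randomisation occurs before 12PM and the first dose of acetazolamide is given before 12PM". A bracket restricting something to the acetazolamide arm follows. It is unclear whether it restricts only the dose condition or the whole sentence.

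Nothing in the protocol gives control patients a matching next-morning time zero.

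**The concern.** Net fluid loss, daily and over 4 days, is a co-primary endpoint and is a quantity per unit of elapsed time. If the window over which it is read starts at a different point in each arm, part of any between-arm difference can come from the visit rules rather than from acetazolamide. Section 7.4 defends the open-label design on the ground that the primary endpoints are not open to bias from unblinded treatment. That defence does not cover a measurement window that itself depends on allocation. The planned regression in Section 10.3.2 adjusts for salt intake and hours of furosemide, not for this offset.

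There is also an operational problem. A control patient randomised in the afternoon may face visit rules that cannot all be met. In addition, the bottle instructions at Visits 2 and 4 time the collection from an acetazolamide dose that controls never receive. Staff would have to improvise, knowing the allocation.

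**Working it through.** The protocol states no figure for this offset, so there is none to reproduce. The check is clock arithmetic plus an illustration from the protocol's own appendix.

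**Inputs**

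- Anchors, the 12PM rule and the 2-hour tolerance: Section 7.8. Morning dosing: Section 8.5. Randomisation at consent: Section 7.3.1.
- Target difference over 4 days: 2 L (Section 10.1).
- Net fluid loss without acetazolamide (Appendix 2, Table 1): TACTICS-HF placebo daily means of 1541, 1419 and 1401 mL on days 1-3; ATHENA-HF standard-care cumulative medians of 1183, 2282, 3810 and 5584 mL at 24, 48, 72 and 96 hours.
- Assumed, because the protocol gives no clock times: randomisation at 12:00-18:00 and first dose at 08:00-12:00 the next day.

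**Step 1: offset between the clocks.** Offset = (24 - hour of randomisation) + hour of first dose next day.

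- Shortest: (24 - 18) + 8 = 14 h.
- Longest: (24 - 12) + 12 = 24 h.
- Worked example, randomised 14:00 and dosed 08:00: (24 - 14) + 8 = 18 h.

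For a same-day morning start the offset is only the lag from randomisation to dose, for example 4 h from 08:00 to 12:00.

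**Step 2: the windows.** At an 18 h offset, measured from randomisation, the control window is 0-96 h and the acetazolamide window is 18-114 h. Both last 96 h. They share 18-96 h and differ only in the first and last 18 h.

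**Step 3: the 12PM rule.**

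- If it binds only the acetazolamide arm, an afternoon control has Visit 2 that afternoon and the Step 1 offset applies in full.
- If it binds both arms, an afternoon control must have Visit 2 the next day but also within 2 h of randomisation. No randomisation time from 12:00 up to 22:00 allows both, since the next day is then more than 2 h away. The 24-hour visit also falls on that same next day.

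Either reading leaves a defect: an offset on the first, a contradiction on the second.

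**Step 4: illustrative size with no drug effect.** Control minus acetazolamide = (offset / 24) x (first-day rate - rate in the last part of the acetazolamide window).

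- TACTICS-HF, days 4 and 5 held at the day 3 value: (18/24) x (1541 - 1401) = 0.75 x 140 = +105 mL. 105 / 2000 = 5%.
- ATHENA-HF increments: 1183; 2282 - 1183 = 1099; 3810 - 2282 = 1528; 5584 - 3810 = 1774. With day 5 held at the day 4 value: (18/24) x (1183 - 1774) = 0.75 x (-591) = -443 mL. 443 / 2000 = 22%.

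| Offset | TACTICS-HF | ATHENA-HF |
|---|---|---|
| 14 h | +82 mL (4%) | -345 mL (17%) |
| 18 h | +105 mL (5%) | -443 mL (22%) |
| 24 h | +140 mL (7%) | -591 mL (30%) |

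Percentages are of the 2 L target. The ATHENA-HF increments are differences between cumulative medians, so they are rough. All values are per affected patient; a difference in trial means would scale with the share of patients affected, which the protocol does not give.

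**The case against.** The best case against runs as follows.

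- **Net fluid loss may not run on the visit clock.** The collections with explicit start and stop hours are for urine electrolytes, a secondary endpoint. Section 11.1 takes net fluid loss from diet sheets and the nursing urine record, Section 7.7 enters intake and output for the previous day, and the diet sheet is completed at 1800. This stands as a limit: fluid balance is listed at the anchored visits, so the protocol implies that window but does not state it.
- **Few patients may be affected.** Only those randomised after midday have the large offset, and their number is unknown. This stands, and it prevents a trial-level estimate.
- **The 12PM rule may bring controls into line.** Perhaps, but on that reading it contradicts the 2-hour rule, so the text still needs repair.

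A reader might also draw stronger conclusions that the protocol does not support:

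- *That controls are observed for less time*, for example 78 h against 96 h, costing about 750 mL at 1000 mL per day. This needs a control baseline taken next morning with the end still set from randomisation. No section says so; within each arm, the start and stop hours use the same anchor.
- *That the bias has a known direction because early diuresis is brisker.* TACTICS-HF shows that pattern. ATHENA-HF, in the same table, shows the reverse.
- *That chloride change is distorted by a calculable amount.* That endpoint is defined by day label, and bloods are listed separately from the timed visit with no clock hour. The appendix rate of -0.6 mmol/L per day comes from patients selected for having developed hypochloraemia, and the -0.9 in Section 10.1 is the change judged clinically meaningful. Neither is a drift rate for controls.

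**Conclusion.** The point holds as an arm-dependent time zero combined with an internal contradiction. For patients randomised after midday the clocks start about 14 to 24 h apart under the assumed clock times or, on the other reading of the 12PM rule, a control's Visit 2 cannot meet both of its timing conditions. The windows differ in start, not length.

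At an 18 h offset, the illustrative effect on 4-day net fluid loss ranges from +105 to -443 mL per affected patient, of either sign. It rests on fluid balance being counted from the visit anchor and on carrying the last available daily figure forward. The protocol supports neither a trial-level bias figure nor a chloride figure. This should be fixed: the likely size is moderate and uncertain, but the rule is wrong as written and would be hard to repair in analysis.

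**What to change.** Define one time zero for both arms, independent of allocation: the planned Day 1 morning time point, recorded in the CRF at randomisation. Run all Visit 2 to 6 assessments, the fluid-balance days and both urine collections from it. Replace the split anchor wherever it appears in Section 7.8, including the bottle instructions at Visits 2 and 4 that refer only to an acetazolamide dose. Reword the 12PM rule so that it clearly applies to both arms and agrees with the 2-hour tolerance. State explicitly that each fluid-balance day starts and ends at this time zero.

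The systematic offset between arms then falls to zero apart from the 2-hour tolerance. The cost is protocol wording and one CRF field, with no extra visits and no change to treatment.
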